#### **9.6.1.2. Sympathetic Nervous System Dysfunction**

Sympathetic nervous system dysfunction will be monitored throughout the study through physical examination, AE reporting, assessment of orthostatic hypotension, and the Survey of Autonomic Symptoms (Section 8.2.3.5). New onset or worsening of signs and symptoms of autonomic dysfunction will be evaluated by the investigator. Sympathetic nervous system dysfunction will only be diagnosed after consultation with an appropriate specialist, such as a neurologist and/or cardiologist.

In cases where new or worsening symptoms consistent with sympathetic nervous system dysfunction are moderate to severe or are clinically significant and do not resolve or return to baseline in 2 weeks (or less at the discretion of the investigator), study drug will be withheld and the patient will be referred to a specialist. If the evaluation by the appropriate specialist does not suggest sympathetic nervous system dysfunction, study drug may be restarted. If the specialist's evaluation does reveal sympathetic nervous system dysfunction then study drug will be permanently discontinued and the case will be reported as an AESI (Section 9.4.3).

Orthostatic hypotension may be a manifestation of sympathetic nervous system dysfunction. If a patient is determined to have orthostatic hypotension, study drug should be withheld and the AE should be entered in the CRF. The following procedures should be followed:

- If the patient is symptomatic and a clinical explanation for orthostatic hypotension is identified (such as a new medication or dehydration due to exercise or illness or excessive heat exposure), study drug will be withheld, and the patient should return to the study site for an unscheduled visit in 1 to 10 days for an unscheduled assessment of orthostatic hypotension.

- If the orthostatic hypotension has resolved, study drug may be restarted.
- If the orthostatic hypotension has not resolved, then study drug will be withheld, and the patient will be referred to a specialist (neurologist or a cardiologist) for evaluation of sympathetic nervous system dysfunction.
  - If the specialist’s evaluation does not reveal new onset sympathetic nervous system dysfunction, including symptoms of bradycardia (lightheadedness), orthostatic hypotension (lightheadedness on standing), syncope, absence of sweating in conditions where sweating would be expected, or if the specialist’s evaluation identifies an alternative cause, such as initiation of a new medication known to cause orthostasis, then study drug may be given at the next visit.
  - If the specialist’s evaluation does reveal sympathetic nervous system dysfunction, then study drug will be permanently discontinued and the case reported as an AESI (Section 9.4.3).
- If the patient has asymptomatic orthostatic hypotension, study drug will be withheld, and the patient should return to the study site for an unscheduled visit in 1 to 10 days for an unscheduled assessment of orthostatic hypotension.
  - If the unscheduled assessment does not reveal orthostatic hypotension then study drug may be continued.
  - If the unscheduled assessment demonstrates orthostatic hypotension then study drug will continue to be withheld until the patient has been evaluated by a specialist (neurologist or a cardiologist) for evidence of sympathetic nervous system dysfunction.
    - If the specialist’s evaluation does not reveal new sympathetic nervous system dysfunction including symptoms of bradycardia (lightheadedness), orthostatic hypotension (lightheadedness on standing), syncope, absence of sweating in conditions where sweating would be expected, or if the specialist’s evaluation identifies an alternative cause such as initiation of a new medication known to cause orthostasis, then study drug may be restarted.
    - If the specialist’s evaluation does reveal sympathetic nervous system dysfunction then study drug will be permanently discontinued and the case reported as an AESI (Section 9.4.3).

### 9.6.1.3. Peripheral Sensory Adverse Events

Altered peripheral sensation (eg, paraesthesia and hypoaesthesia) is an important identified risk with fasinumab (see Investigator’s Brochure) and other anti-NGF compounds. Any peripheral sensory AE that, per the investigator’s judgment, requires a neurology or other specialty consultation must be reported as an AESI. If any peripheral sensory event persists for 2 months the patient must be referred for a neurology or other specialty consultation and the event must be reported as an AESI (Section 9.4.3).

#### 9.6.1.4. Joint Replacement Surgery

An end of study phone contact will be conducted at 52 weeks following the last dose of study drug to evaluate the number of patients who have undergone or are scheduled for JR surgery as described in Section 8.2.3.9. Any elective JR surgery planned before completion of the ICF would be part of the exclusion criteria and would not be considered an AE.

After signing of the ICF, report JR surgery as an AESI if the JR surgery is an elective event that is not associated with a new/worsening AE.

Do not report JR surgery as an AE/AESI if the JR surgery is for the treatment of a new or worsening AE. In this case, the new or worsening AE should be the reported AE/AESI term.

### 9.7. Investigator Alert Notification

Regeneron (or designee) will inform all investigators participating in this clinical trial, as well as in any other clinical trial using the same investigational drug, of any SAE that meets the relevant requirements for expedited reporting (an AE that is serious, unexpected based on the Investigator's Brochure or this protocol, and has a reasonable suspected causal relationship to the medicinal/study drug).

## 10. STATISTICAL PLAN

This section provides the basis for the statistical analysis plan (SAP) for the study. The SAP may be revised during the study to accommodate amendments to the clinical study protocol and to make changes to adapt to unexpected issues in study execution and data that may affect the planned analyses. The final SAP will be issued before the database is locked.

Analysis variables are listed in Section 4.

### 10.1. Statistical Hypothesis

There are 6 hypotheses for the primary and key secondary endpoints. The primary treatment comparison for the WOMAC pain and physical function subscale scores is declared superior only if the comparisons are significant for both WOMAC pain and physical function subscale scores. The sequentially rejective multiple test procedure (Bretz 2009) will be applied to control for multiplicity and to maintain study-wise Type I error rate at two-sided 0.05 level for the hypotheses ( $H_i$ ,  $i=1, \dots, 6$  for fasinumab 1 mg Q4W) for the primary and key secondary endpoints. The primary hypothesis will be tested at 0.05 level. If the primary hypothesis is rejected, the alpha level will be reallocated to other hypotheses according to the pre-specified procedure. The testing will stop when no hypothesis can be rejected at any step. Details will be provided a priori in the SAP.

- $H_1$ : There is no treatment difference between fasinumab 1 mg Q4W and placebo in WOMAC pain or physical function subscale scores at week 24 versus there is treatment difference in WOMAC pain and physical function subscale scores at week 24
- $H_2$ : There is no treatment difference between fasinumab 1 mg Q4W and placebo in Patient Global Assessment score at week 24 versus there is treatment difference in Patient Global Assessment score at week 24

- H3: There is no treatment difference between fasinumab 1 mg Q4W and placebo in the proportion of patients with  $\geq 30\%$  improvement in the WOMAC pain subscale scores at week 24 versus there is treatment difference in proportion of patients with  $\geq 30\%$  improvement in WOMAC pain at week 24
- H4: There is no treatment difference between fasinumab 1 mg Q4W and NSAIDs in the WOMAC pain subscale scores at week 24 versus there is treatment difference in WOMAC pain subscale scores at week 24
- H5: There is no treatment difference between fasinumab 1 mg Q4W and NSAIDs in the WOMAC physical function subscale scores at week 24 versus there is treatment difference in WOMAC physical function subscale scores at week 24
- H6: There is no treatment difference between fasinumab 1 mg Q4W and NSAIDs in Patient Global Assessment score at week 24 versus there is treatment difference in Patient Global Assessment score at week 24

## 10.2. Justification of Sample Size

Assuming a 2-sided alpha level 0.05 and a 20% dropout rate up to week 24, an enrollment of 600 patients in the fasinumab 1 mg Q4W group and 300 patients in the placebo group will provide at least 99% power to detect an effect size of 0.46 in the WOMAC pain and physical function subscale scores (ie, absolute treatment difference of 1.1 between fasinumab and placebo with a SD of 2.4). The assumed treatment difference and standard deviation (SD) are based on results from study R475-PN-1227. The sample size will provide 99% power to detect an effect size of 0.36 in PGA (ie, absolute treatment difference of 0.4 with a SD of 1.1, R475-PN-1227).

Assuming a 2-sided alpha level 0.05 and a 20% dropout rate up to week 24, an enrollment of 600 patients in the fasinumab 1 mg Q4W group and the pooled NSAIDs group will provide approximately 92% power to detect an effect size of 0.22 in the WOMAC pain subscale (ie, absolute treatment difference of 0.51 with a SD of 2.3, [Schnitzer 2015]). The sample size will provide 95% power to detect an effect size of 0.24 in WOMAC physical function subscale (ie, absolute treatment difference of 0.50 with a SD of 2.1, [Schnitzer 2015]), and 79% power to detect an effect size of 0.18 in PGA (ie, absolute treatment difference of 0.18 with a SD of 1.0 [Ekman 2014]).

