## 6. SELECTION, WITHDRAWAL, AND REPLACEMENT OF PATIENTS

### 6.1. Number of Patients Planned

The sample size for this study has been revised from 2700 patients in the previous amendments to approximately 1620 patients in amendment 4 due to the discontinuation of fasinumab 3 mg Q4W and 6 mg Q8W dose regimens. There will be approximately 600 patients randomized to the fasinumab 1 mg SC Q4W group, 300 patients randomized to the each of the NSAID groups, and 300 patients randomized to the placebo group (a total of 1500 patients). In addition, approximately, 60 patients each were enrolled in the fasinumab 3 mg SC Q4W and 6 mg SC Q8W groups prior to the implementation of the urgent safety measure to discontinue these doses.

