### 2.2. Sample Size and Power Considerations

Assuming a 2-sided alpha level of 0.05 and a 20% dropout rate up to week 24, an enrollment of 600 patients in the fasinumab 1 mg Q4W group and 300 patients in the placebo group will provide at least 99% power to detect an effect size of 0.46 in the WOMAC pain and physical function subscale scores (i.e., absolute treatment difference of 1.1 between fasinumab and placebo with a SD of 2.4). The assumed treatment difference and standard deviation (SD) are based on results from study R475-PN-1227. The sample size will provide 99% power to detect

an effect size of 0.36 in PGA (i.e., absolute treatment difference of 0.4 with a SD of 1.1, R475-PN-1227).

Assuming a 2-sided alpha level 0.05 and a 20% dropout rate up to week 24, an enrollment of 600 patients in the fasinumab 1 mg Q4W group and the pooled NSAIDs group will provide approximately 92% power to detect an effect size of 0.22 in the WOMAC pain subscale (i.e., absolute treatment difference of 0.51 with a SD of 2.3, [Schnitzer 2015]). The sample size will provide 95% power to detect an effect size of 0.24 in WOMAC physical function subscale (i.e., absolute treatment difference of 0.50 with a SD of 2.1, [Schnitzer 2015]), and 79% power to detect an effect size of 0.18 in PGA (i.e., absolute treatment difference of 0.18 with a SD of 1.0 [Ekman 2014]).

The sample size has been revised from 2700 patients in the previous amendments to approximately 1620 patients in amendment 4 due to the discontinuation of fasinumab 3 mg Q4W and 6 mg Q8W dose regimens. There will be approximately 600 patients randomized to the fasinumab 1 mg SC Q4W group, 300 patients randomized to the each of the NSAID groups, and 300 patients randomized to the placebo group (a total of 1500 patients). In addition, approximately 60 patients each were enrolled in the fasinumab 3 mg SC Q4W and 6 mg SC Q8W groups under earlier versions of the protocol before dosing was discontinued in these treatment groups.

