#### 5.7.4. Adjustment for Multiple Comparison

To control the overall Type I Error of the clinical trial at 5%, the sequentially rejective multiple test procedure (Bretz 2009) will be applied. Hypothesis H1 will be tested at  $\alpha_0 = 0.05$ . As it is a hypothesis test concerning the co-primary endpoints, the hypothesis will be rejected if the following is met:

- The hypothesis of no treatment difference between fasinumab 1 mg Q4W and placebo in WOMAC pain subscale at week 24 is rejected  $\alpha_0 = 0.05$

AND

- The hypothesis of no treatment difference between fasinumab 1 mg Q4W and placebo in WOMAC physical function subscale at week 24 between fasinumab and placebo is rejected  $\alpha_0 = 0.05$

If a hypothesis is rejected, the alpha level for that hypothesis will be reallocated to other hypothesis according to the graph. The graph will be updated according to the pre-specified algorithm, as described by Bretz 2009. The rest of the hypotheses will be tested at the updated alpha level based on the updated graph. The testing will stop when no hypothesis can be rejected at any step.

If the primary analysis of efficacy is successful, secondary endpoints will be tested according to hierarchical testing strategy based on the following order:

H3 → H2 → H4 → H5 → H6

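### The 92%, 95% and 79% powers for the NSAID comparisons are single-test figures; under the SAP's fixed order H5 cannot have more power than H4, so 95% is not attainable

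*Protocol*

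**What the plan says.** Protocol 10.2 powers the three comparisons of fasinumab with the pooled NSAID group under one set of conditions: "Assuming a 2-sided alpha level 0.05 and a 20% dropout rate up to week 24", with "600 patients in the fasinumab 1 mg Q4W group and the pooled NSAIDs group". The pooled group is two arms, since Protocol 6.1 plans "300 patients randomized to the each of the NSAID groups". It then gives "approximately 92% power to detect an effect size of 0.22 in the WOMAC pain subscale" (H4), "95% power to detect an effect size of 0.24 in WOMAC physical function subscale" (H5) and 79% for Patient Global Assessment (H6). SAP 2.2 repeats these values, including "79% power to detect an effect size of 0.18 in PGA".

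Protocol 10.1 names a sequentially rejective procedure and leaves its details to the SAP. SAP 5.7.4 supplies them: H1 is tested at 0.05, and if it succeeds "secondary endpoints will be tested according to hierarchical testing strategy based on the following order": H3, H2, H4, H5, H6. Testing ends once nothing further can be rejected. Neither document gives a power under this sequence, and neither gives any power for H3.

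**The concern.** In a fixed sequence, rejecting H5 requires that H4 has already been rejected. The event that H5 is rejected lies inside the event that H4 is rejected, so it cannot be more probable. A stated 95% for H5 beside a stated 92% for H4 conflicts with that order. H6 sits one step further down and needs both H4 and H5.

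H4 to H6 are the only NSAID comparisons under multiplicity control, and they carry the first secondary objective. A reader of SAP 2.2 would take 95% as the chance that the trial establishes the function claim against NSAIDs. The procedure in SAP 5.7.4 does not provide that chance.

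**Working it through.** **Inputs.** From Protocol 10.2, repeated in SAP 2.2: two-sided alpha 0.05; 600 per group less 20% dropout, so 600 × 0.8 = 480; difference and SD of 0.51 and 2.3 (H4), 0.50 and 2.1 (H5), 0.18 and 1.0 (H6). From SAP 5.7.4: the testing order. Correlations between the test statistics are not in the documents and are assumed below.

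**1. Reproduce the stated figures.** Power = Φ(δ / (SD × √(2/480)) − 1.960), with √(2/480) = 0.06455.

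- H4: 0.51 / (2.3 × 0.06455) = 3.435; Φ(1.475) = 93.0% (stated: about 92%)
- H5: 0.50 / (2.1 × 0.06455) = 3.689; Φ(1.729) = 95.8% (stated: 95%)
- H6: 0.18 / 0.06455 = 2.789; Φ(0.829) = 79.6% (stated: 79%)

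All three agree to about a point. Leaving out dropout would give 97.0%, 98.5% and 87.7%, which does not fit. The stated values are therefore single-test powers at the full 0.05.

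**2. Ceiling for H5.** P(reject H5 in sequence) = P(H1, H3, H2, H4 and H5 all rejected) ≤ P(reject H4). This is 92% on the stated figure and 93.0% recomputed. Both are below 95%, and no correlation changes that.

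**3. Ceiling for H6.** P(reject H6 in sequence) is at most the smallest single-test power among the hypotheses up to and including H6. Among H4 to H6 that is H6's own, 79% stated or 79.6% recomputed. The stated 79% is thus a limit, approached only when the tests are almost perfectly correlated.

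**4. Size under assumed correlations.** The three statistics are taken as jointly normal with the means from step 1, and H1, H3 and H2 as always rejected. The independent case is a simple product: 0.9299 × 0.9581 = 0.891 for H5, and × 0.7963 = 0.710 for H6.

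| Pain–function correlation | Correlation of each with PGA | H5, recomputed | H6, recomputed | H5, from stated 92/95/79% | H6, from stated 92/95/79% |
|---|---|---|---|---|---|
| 0 | 0 | 0.891 | 0.710 | 0.874 | 0.691 |
| 0.5 | 0.3 | 0.902 | 0.736 | 0.887 | 0.721 |
| 0.8 | 0.5 | 0.915 | 0.758 | 0.902 | 0.745 |
| 0.9 | 0.7 | 0.921 | 0.776 | 0.910 | 0.766 |
| 0.95 | 0.8 | 0.926 | 0.785 | 0.915 | 0.776 |

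**5. Earlier tests.** With 480 against 240, the same formula gives Φ(1.1 / (2.4 × 0.07906) − 1.960) > 99.9% for each half of H1, and Φ(0.4 / (1.1 × 0.07906) − 1.960) = 99.6% for H2, where √(1/480 + 1/240) = 0.07906. A simulation of 200,000 trials added H1, H2 and the shared fasinumab arm, with pain–function correlation 0 to 0.95 and PGA correlations at 0.75 of that. It gave 88.7% to 92.2% for H5 and 70.8% to 77.6% for H6, so H1 and H2 cost little. H3 cannot be added from the documents. Any H3 power below 1 can only lower, never raise, the figures for H4, H5 and H6.

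**The case against.** The strongest reply is that nothing has been miscalculated. Protocol 10.2 states alpha, dropout, effect and SD for each comparison, and the power that follows is right for that comparison alone. Reporting power per comparison for secondary endpoints and describing the testing strategy elsewhere is common. The protocol section also contains no order; the conflict appears only once SAP 5.7.4 is read with it. This stands, and it rules out calling the point an arithmetic error. It does not remove the point, because SAP 2.2 repeats the 95% without qualification in the same document that makes H5 conditional on H4, and the protocol had left the testing details to the SAP.

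A reader might also infer that the 79% for H6 is unattainable in the same way. The documents do not support that: 79% is below the powers of H4 and H5, and how far the sequence power falls short depends on correlations they do not give. For the same reason, single replacement values such as 91% for H5 or 76% for H6 would carry more precision than the plan allows.

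Finally, the loss is small, concerns secondary endpoints only, and could be matched by the approximation of a two-sample formula to an MMRM with multiple imputation. That is fair on materiality. The ceiling itself does not depend on the approximation: under any analysis model H5 cannot be rejected more often than H4.

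**Conclusion.** The point holds as a matter of labelling and consistency. The 92%, 95% and 79% are correct single-test powers that are not described as such. Under SAP 5.7.4 the power for H5 is at most that of H4 (92% stated, about 93% recomputed), so 95% overstates it by at least 2 to 3 points. That part needs no assumption beyond the documents. With correlations of 0 to 0.95 assumed, H5 is roughly 89–93%, some 2 to 6 points below 95%. H6 is at most 79% (79.6% recomputed) and roughly 71–79% with pain–function correlation up to 0.95 and PGA correlations up to 0.8. These ranges use the recomputed powers; starting from the rounded stated values lowers them by about 1 to 2 points. All treat H3 as certain to be rejected, so they are upper values.

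It would be wrong to infer that the trial is too small for its primary aim or that Type I error is at risk. Recomputed power for each half of H1 exceeds 99.9%, and the full 0.05 passes down the sequence, so no alpha correction is needed.

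**What to change.** In SAP 2.2:

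- Label 92%, 95% and 79% as powers of single tests at two-sided 0.05 that take no account of the testing order in SAP 5.7.4.
- Add that under that order H5 power is at most H4's (about 92–93%; roughly 89–93% for test correlations of 0 to 0.95), and H6 power is at most 79% (roughly 71–79% over the same pain–function range, with the PGA correlations used).
- Mark the correlations as assumptions. Note that H3's power is not stated and was taken as 1, so the figures are upper values; if the sponsor has a basis for an H3 power, state it and carry it through.

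The cost is two or three sentences and slightly less favourable figures. Sample size, alpha, testing order and analysis stay as they are. If the protocol is amended for other reasons, the same label can go into section 10.2 and the synopsis.

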## 10.3. Analysis Sets

### 10.3.1. Efficacy Analysis Sets

The full analysis set (FAS) includes all randomized patients and is based on the treatment allocated (as randomized). Efficacy endpoints will be analyzed using the FAS including patients randomized to fasinumab 1 mg Q4W, NSAIDs, and placebo. Efficacy data from patients randomized to fasinumab 3 mg Q4W or 6 mg Q8W will not be included in the analysis, but will be summarized descriptively in separate tables.

### 10.3.2. Safety Analysis Set

The safety analysis set (SAF) includes all randomized patients who received any study drug; it is based on the treatment received (as treated). Treatment compliance/administration and all clinical

safety variables will be analyzed using the SAF including patients randomized to fasinumab 1 mg Q4W, NSAIDs, and placebo. Safety data from patients randomized to fasinumab 3 mg Q4W or 6 mg Q8W will not be included in the main safety analysis summaries, but will be summarized in separate tables.

### **10.3.3. Per-Protocol Set**

The per protocol set (PPS) will include all randomized patients who complete the 24-week treatment period and who do not have to be excluded due to major protocol deviations. The PPS will be used to perform sensitivity analyses for the primary and selected secondary endpoints.

### **10.3.4. Pharmacokinetic Analysis Set**

The PK analysis population includes all treated patients who received any study drug and who had at least 1 non-missing drug concentration result following the first study dose.

### **10.3.5. Anti-Drug Antibody Analysis Set**

The ADA analysis population includes all treated patients who had at least 1 non-missing ADA result following the first study dose.

## **10.4. Statistical Methods**

### **10.4.1. Patient Disposition**

The following will be provided:

- The total number of screened patients: met the inclusion criteria regarding the target indication and signed the ICF
- The total number of randomized patients: received a randomization number
- The total number of patients in each analysis set
- The total number of patients who discontinued the study, and the reasons for discontinuation
- A listing of patients treated but not randomized, patients randomized but not treated, and patients randomized but not treated as randomized
- A listing of patients prematurely discontinued from treatment, along with reasons for discontinuation

